**Appendix 2: Continuation of Appendix 1 Schedule of Events (Subjects with Subsequent CIT Transplants)**

Subjects who receive a subsequent islet transplant should continue their study visits according to this Schedule of Events until one year (365 +/- 5 days) after the final islet transplant. Additional visits - outlined in Appendix 3 - will also need to be completed after each subsequent transplant. After day 365 post final transplant, subjects should stop following this schedule, and complete the follow-up visits outlined in Appendix 4: *Schedule of Events for 1-Year Additional Follow-Up*.

Time points (in days relative to 1 st transplant)	392	420	448	476	504	532	560	588	616
Visit Number	22	23	24	25	26	27	28	29	30
Visit Windows (in days)	±5	±5	±5	±5	±5	±5	±5	±5	±5
Equivalent Week	W56	W60	W64	W68	W72	W76	W80	W84	W88
GENERAL ASSESSMENTS									
Physical Exam			X			X			X
QOL			X			X			X
AE/Hypo Event/Toxicity Assessment	X	X	X	X	X	X	X	X	X
LOCAL LABORATORY ASSESSMENTS									
CBC (WBC + Diff & Plat)			X			X			X
Chemistry 			X			X			X
Lipids			X			X			X
Pregnancy test (WOCBP) 	X	X	X	X	X	X	X	X	X
CENTRAL LABORATORY ASSESSMENT									
HbA1c			X			X			X
Fasting serum glucose & c-peptide & serum creat 	X	X	X	X	X	X	X	X	X
90 min  c-peptide/glucose (MMTT) 			X			X			X
Atherogenic Profile 	1 year post-final transplant								
LOCAL METABOLIC ASSESSMENTS									
BSR eCRFs 			X			X			X
CALCULATED METABOLIC ASSESSMENTS									
MAGE			X			X			X
LI			X			X			X
Clarke Score						X			
HYPO			X			X			X

Time points (in days relative to 1 st transplant)	392	420	448	476	504	532	560	588	616
Visit Number	22	23	24	25	26	27	28	29	30
Visit Windows (in days)	±5	±5	±5	±5	±5	±5	±5	±5	±5
Equivalent Week	W56	W60	W64	W68	W72	W76	W80	W84	W88
CALCULATED METABOLIC ASSESSMENTS (continued)									
Beta Score			X			X			X
C-peptide (glucose X creatinine) ratio	X	X	X	X	X	X	X	X	X
IMMUNOSUPPRESSION LEVELS									
Belatacept trough levels 	X	X	X	X	X	X	X	X	X
MECHANISTIC ASSAYS									
Alloantibodies 			X			X			X
Autoantibodies 			X			X			X
Immunogenicity samples 						X			
ARCHIVED SAMPLES									
Serum			X			X			X
Plasma			X			X			X

 EBV by PCR should only be done post-randomization if reactivation is suspected.

 Chemistry includes: Sodium, albumin, magnesium, chloride, potassium, alk phosphatase, total bilirubin, CO2, creatinine, ALT (SGPT), BUN, gamma GT, glucose, AST (SGOT), calcium, phosphorus

 Confirm negative result prior to administering Belatacept.

 Also collect as necessary to perform graft failure. Do not collect after graft failure has been confirmed.

 MMTT should include 90 minute c-peptide and glucose measurements, add 60 minute as necessary when determining graft failure.

 Atherogenic profile consisting of fasting lipid panel (TG, TC, HDL, LDL, non-HDL), C reactive protein, serum amyloid A, apolipoprotein A1 and apolipoprotein B. If blood is drawn locally, sample should be sent from local lab to study site and then shipped to the central laboratory (Univ of Washington).

 Blood sugar Record (BSR) eCRF is completed using information gathered from subject diary logs, glucometer download data, and insulin requirements.

 Complete test prior to Belatacept infusion. For pregnancy test, confirm negative result prior to administering Belatacept.

 For each transplant, complete alloantibody assessment every 6 months and again on Day -2, regardless of the most recent draw.

 Autoantibody testing includes GAD, IA-2, and IAA.

 Collect immunogenicity samples prior to belatacept infusion. For subjects that discontinue belatacept, collect additional immunogenicity samples at 4 weeks and 8 weeks post last dose.

**Appendix 3: Subsequent Transplant Schedule of Events**

The following immediate post-transplant and endpoint assessments should be completed for subjects who receive a subsequent islet transplant. If any of the visits below fall within an acceptable window of a follow-up visit on the Year One Schedule of Events (Appendix 1) or Year Two Schedule of Events (Appendix 2), the assessments may be added to that follow-up visit so that a separate visit does not need to occur.

Time point (in days relative to most recent infusion)	0 	3	4	7	75	365
Visit Number	TBD	TBD	TBD	TBD	TBD	TBD
Visit Window (in days)	N/A	N/A	N/A	+/- 3	+/- 5	+/- 14
Equivalent Week (post most recent infusion)	N/A	N/A	N/A	W1	N/A	W52
GENERAL ASSESSMENTS						
Physical Exam	X			X	X	X
QOL					X	X
Chest X-Ray						X
Abdominal US (Pelvis/Liver)				X		X
ECG						X
PPD						X
AE/Hypo Event/Toxicity Assess	X		X	X	X	X
LOCAL LABORATORY ASSESSMENTS						
CBC (WBC + Diff & Plat)	X			X	X	X
Chemistry 	X			X	X	X
Lipids					X	X
Coagulation (PT, PTT, INR)	X					
Blood Type & HLA	X 					
Crossmatch	X 					
PRA by flow cytometry	X 					
Fasting & post-prandial c-peptide 		X		X		
Glucose (immediately post-transplant) 	X					
Pregnancy test (WOCBP) 	X					X
CMV by PCR 					X	
CENTRAL LABORATORY ASSESSMENTS						
First morning spot urine 					X	X
GFR					X	X
HbA1c					X	X
Fasting serum glucose/c-peptide & creat 					X	X
Insulin modified FSIGT 					X	X
90 min c-pep/ glucose (MMIT) 					X	X
Artherogenic Profile 						X
LOCAL METABOLIC ASSESSMENTS						
Glycemic Stability (CGMS) 					X	X
BSR eCRFs 					X	X
CALCULATED METABOLIC ASSESSMENTS						
MAGE					X	X
LI					X	X
Clarke Score						X
HYPO					X	X
Beta Score					X	X

Time point (in days relative to most recent infusion)	0 	3	4	7	75	365
Visit Number	TBD	TBD	TBD	TBD	TBD	TBD
Visit Window (in days)	N/A	N/A	N/A	+/- 3	+/- 5	+/- 14
Equivalent Week (post most recent infusion)	N/A	N/A	N/A	W1	N/A	W52
CALCULATED METABOLIC ASSESSMENTS (continued)						
C-peptide glucose creatinine ratio					X	X
IMMUNOSUPPRESSION LEVELS						
Belatacept trough levels 			X	X	X	X
MECHANISTIC ASSAYS						
Alloantibody 	X				X	X
Autoantibody 					X	X
Immunogenicity samples 						X
ARCHIVED SAMPLES						
Serum					X	X
Plasma					X	X

 Day 0 = the day of transplant.

 Chemistry includes: Sodium, albumin, magnesium, chloride, potassium, alk phosphatase, total bilirubin, CO2, creatinine, ALT (SGPT), BUN, gamma GT, glucose, AST (SGOT), calcium, phosphorus

 Repeat for subsequent transplant(s).

 Sample used for crossmatch may be obtained up to 60 days prior to islet infusion, as long as there is no evidence of infections or transfusions since the time the sample was drawn.

 PRA by flow cytometry should be performed locally prior to any subsequent transplant. Local result used to determine eligibility for subsequent transplants only.

 C-peptide should be done locally and drawn fasting, and twice between 1-3 hrs post-prandial on Day 3 and Day 7 post-transplant.

 Finger stick glucose should be done locally and drawn every hour for the first 6 hours immediately post-transplant.

 Perform pregnancy test and confirm negative result prior to each belatacept infusion.

 EBV by PCR should only be done post-randomization if reactivation is suspected.

 First morning spot urine includes: albumin, protein, and creatinine.

 Also collect as necessary to confirm graft failure. Do not collect after graft failure has been confirmed.

 Atherogenic profile consisting of fasting lipid panel (TG, TC, HDL, LDL, non-HDL), C reactive protein, serum amyloid A, apolipoprotein A1 and apolipoprotein B. If blood is drawn locally, sample should be sent from local lab to study site and then shipped to the central laboratory (Univ of Washington).

 Blood Sugar Record (BSR) eCRF is completed using information gathered from subject diary logs, glucometer download data, and insulin requirements.

 Complete test prior to belatacept infusion. For pregnancy test, confirm negative result prior to administering belatacept.

 For each transplant, complete alloantibody assessment every 6 months and again on Day -2, regardless of the most recent draw.

 Autoantibody testing includes GAD, IA-2, and IAA.

 Collect immunogenicity samples prior to belatacept infusion. For subjects that discontinue belatacept, collect additional immunogenicity samples at 4 weeks and 8 weeks post last dose.

*Appendix 4: Schedule of Events for 1-Year Additional Follow-Up*

Time point (Equivalent weeks after 'Day 365 post final transplant' visit)	W4 (AY)	W8 (AY)	W12 (AY)	W16 (AY)	W20 (AY)	W24 (AY)	W28 (AY)	W32 (AY)	W36 (AY)	W40 (AY)	W44 (AY)	W48 (AY)	W52 (AY)	Y2  (AY)
Visit Number (relative to final islet transplant)	51	52	53	54	55	56	57	58	59	60	61	62	63	64
Visit Window (specified in days)	±5	±5	±5	±5	±5	±5	±5	±5	±5	±5	±5	±5	±5	±30
GENERAL ASSESSMENTS														
Physical Exam						X							X	X
Telephone Consult			X							X				
QOL													X	X
AE /Hypoglycemic Events/Toxicity Assessment			X			X				X			X	X
LOCAL LABORATORY ASSESSMENTS														
CBC (WBC + Diff & Plat)			X			X				X			X	
Chemistry 			X			X				X			X	
Lipids						X							X	
Pregnancy test (WOCBP) 	X	X	X	X	X	X	X	X	X	X	X	X	X	
CENTRAL LABORATORY ASSESSMENTS														
First morning spot urine 						X							X	
GFR													X	
HbA1c			X 			X				X 			X	X
90-min c-pep/glucose (MMIT) 						X							X	X
Atherogenic Profile													X	
LOCAL METABOLIC ASSESSMENTS														
Glycemic Stability (CGMS) 													X	X

 Two years post initial transplant.

 Also collect as necessary to confirm graft failure. Do not collect after graft failure is confirmed.

Time point (Equivalent weeks after 'Day 365 post final transplant' visit)	W4 (AY)	W8 (AY)	W12 (AY)	W16 (AY)	W20 (AY)	W24 (AY)	W28 (AY)	W32 (AY)	W36 (AY)	W40 (AY)	W44 (AY)	W48 (AY)	W52 (AY)	Y2  (AY)
Visit Number (relative to final islet transplant)	51	52	53	54	55	56	57	58	59	60	61	62	63	64
Visit Window (specified in days)	±5	±5	±5	±5	±5	±5	±5	±5	±5	±5	±5	±5	±5	±30
CALCULATED METABOLIC ASSESSMENTS														
Clarke Score													X	
IMMUNOSUPPRESSION LEVELS														
Belatacept Trough Levels	X	X	X	X	X	X	X	X	X	X	X	X	X	
MECHANISTIC ASSAYS														
Autoantibody						X							X	
MECHANISTIC ASSAYS (Cont'd)														
Alloantibody						X							X	
Immunogenicity Samples													X	X

 Since belatacept is infused every 28 days, an additional infusion visit will be required during the second year. Since the timing is dependent on final transplant date, this visit can be shifted as needed.

 Chemistry includes: Sodium, albumin, magnesium, chloride, potassium, alk phosphatase, total bilirubin, CO2, creatinine, ALT (SGPT), BUN, gamma GT, glucose, AST (SGOT), calcium, phosphorus.

 Perform pregnancy test and confirm negative result prior to each belatacept infusion.

 First morning spot urine includes: albumin, protein, and creatinine.

 Can be drawn locally.

### *Appendix 5: Reduced Follow-up Schedule of Events*

Subjects withdrawn from study therapy should be followed according to the reduced follow-up schedule provided below. All reduced follow-up assessments should be scheduled relative to the day on which the study treatment is discontinued. The last follow-up visit will vary depending on when the subject discontinues study therapy and should be done at 1 year post the subject's **last** transplant.

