#### **Potential Risks in Renal Transplantation**

##### *Post-transplant Lymphoproliferative Disorder*

In the combined BMS-sponsored Phase 2 (median exposure 74 to 88 months) and Phase 3 studies (median exposure of approximately 39 months) in de novo renal transplantation, post-transplant lymphoproliferative disorder (PTLD) developed more frequently in patients who received belatacept (14 cases out of 949; 1.5% of subjects) than those who received cyclosporine (3 cases out of 476; 0.6%). Of the PTLD cases reported with belatacept, all but 1 occurred during the first 18 months post transplant. More than half of the PTLD cases in belatacept-treated patients involved the CNS (9 cases out of 14; 65% of belatacept patients). A total of 8 out of 14 patients with PTLD in the belatacept group and 3 out of 3 in the cyclosporine group have died.

The excess risk of PTLD with belatacept was concentrated in EBV negative recipients (approximately 10-fold higher than that observed in EBV positive recipients). While there was also an increased risk in EBV positive subjects with belatacept compared to CsA within the studies, the absolute risk in this population was low. In addition to EBV-negative serostatus, CMV disease, and use of lymphocyte depleting therapy for treatment of AR were also associated with an increased risk of PTLD in the core belatacept studies. Nonetheless, the highest risk of PTLD with belatacept was observed in EBV-negative subjects. Thus, belatacept should not be administered to belatacept naïve patients who are EBV-negative or have unknown EBV serostatus. PTLD should be considered in subjects who develop new neurologic signs or symptoms.

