#### 5.7.2 Premature Discontinuation of Study Treatment (Transition to “Off-Protocol” Treatment)

Study treatment may be prematurely discontinued for any subject for any of the following reasons:

1. The subject is unwilling or unable to comply with the protocol.
2. The investigator believes that the study treatment is no longer in the best interest of the subject.
3. Graft Failure (see Study Definitions).
4. Any clinical AE, laboratory abnormality, or intercurrent illness which, in the opinion of the investigator, indicates that continued treatment with study therapy is not in the best interest of the subject. The agent(s) to which the event is attributed will be discontinued.
5. The subject becomes pregnant
6. Missing 2 consecutive belatacept infusions
7. The development of belatacept is terminated by the manufacturer (BMS)
8. The subject is imprisoned or compulsorily detained for the treatment of either a psychiatric or physical illness (e.g., infectious disease).

Subjects who prematurely discontinue study treatment will remain in the study until normal termination, for the purpose of monitoring safety and efficacy parameters and will enter the reduced follow-up scheduled outlined in Appendix 5. Data from these subjects will be used in the intent-to-treat analysis. These subjects are permitted to simultaneously enroll in a CIT or site-specific graft failure follow-up protocol, if available.

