## 6. CRITERIA FOR SUBJECT WITHDRAWAL AND PREMATURE TERMINATION OF THE STUDY

### 6.1 Subject Withdrawal Criteria

Subjects may be prematurely terminated from study for the following reasons:

1. The subject elects to withdraw consent from all future study activities, including follow-up.
2. The subject is "lost to follow-up" (i.e., no further follow-up is possible because attempts to reestablish contact with the subject have failed).
3. The subject develops a clinical AE, laboratory abnormality, or intercurrent illness which, in the opinion of the investigator, indicates that continued treatment with study therapy and further participation in the study (including obtaining vital status of the subject and islet graft) is not in the best interest of the subject.
4. The development of belatacept is terminated by the manufacturer (BMS).
5. The subject becomes a prisoner or becomes involuntarily incarcerated for treatment of either a psychiatric or physical (e.g., infectious disease) illness.
6. The subject dies.

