#### **REDUCED FOLLOW-UP SCHEDULE**

Complete the following assessments at the intervals (+/- 7 days) indicated below relative to the day the subject discontinued study treatment. Continue conducting these assessments at the defined intervals until the subject reaches two years post **last** transplant.

- Assess SAEs and hypoglycemic events: q1 month. If subject does not come to the study site for the visit, attempt to obtain information via a phone contact.
- Alloantibody (central lab): q 1 month for the first 3 months and q 3 months thereafter.
- Immunogenicity Samples: for subjects who discontinue belatacept, collect samples at 4 weeks and 8 weeks post last dose

Complete the following assessments at 1 and 2 years (+/- 14 days) post **initial** transplant:

- Assess SAEs and hypoglycemic events
- Alloantibody (central lab)
- HbA1c (central lab)
- 90 minute c-peptide post MMTT (central lab)
- Serum creatinine (central lab)
- QOL questionnaire (via mail or in-person)

Complete the following assessments at 1 and 2 years (+/- 7 days) post **last** transplant:

- Assess SAEs and hypoglycemic events
- QOL questionnaire (via mail or in-person)

*Appendix 6: Study Contacts*

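### Appendix 5 ends reduced follow-up at both 1 year and 2 years after the last transplant, and Sections 5.7.2 and 6.1 treat two of the same events differently

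*Protocol*

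**What the plan says.** Appendix 5 governs follow-up of subjects withdrawn from study therapy. Sections 5.7.1.2 and 7.6 also send to it subjects with graft failure who will have no further transplant, and those who do not meet the criteria for one.

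- **Appendix 5, opening paragraph:** the last follow-up visit varies with the time of discontinuation and "should be done at 1 year post the subject's" last transplant.
- **Appendix 5, Reduced Follow-up Schedule:** "Assess SAEs and hypoglycemic events: q1 month", with alloantibody monthly for three months and then every three months. It adds: "Continue conducting these assessments at the defined intervals until the subject reaches two years post" last transplant. It then lists assessments at 1 and 2 years after the initial transplant and at 1 and 2 years after the last.
- **Section 5.7.2:** "Subjects who prematurely discontinue study treatment will remain in the study until normal termination", on the Appendix 5 schedule, and their data enter the intent-to-treat analysis.
- **Section 7.5:** follow-up lasts 24 months after the final transplant.
- **Sections 4.1.2.1 and 4.1.2.2:** severe hypoglycemic events are counted from day 28 to two years. Adverse events and immune sensitization are assessed at two years after the final transplant, among other times.
- **Section 6.1:** "Subjects may be prematurely terminated from study for the following reasons". Items 4 and 5 are the manufacturer ending belatacept development, and imprisonment or involuntary detention. The same two events are items 7 and 8 of Section 5.7.2.
- **Sections 8.2.1 and 8.3.1:** adverse events are collected for 56 days after premature withdrawal. SAEs are collected until 56 days after completion or withdrawal, and after that only if believed related to the investigational agent.
- **Section 8.2.2:** deaths, graft losses, malignancies, PTLD and serious infections are reportable for all randomized subjects to study end, even if study drug has stopped.

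**The concern.** Two end dates for the same subjects cannot both be followed. A coordinator who reads only the opening paragraph would schedule a final visit at 12 months and close the subject, although the two-year endpoints and the intent-to-treat statement assume that data continue to 24 months.

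The subjects affected have stopped treatment or lost the graft, and sensitization matters most in that group. Section 1.5.1.3 reports PRA above 20% in roughly 84% of recipients who had lost islet function and stopped immunosuppression, against about 25% on maintenance. With 10 subjects planned, each one closed early removes a tenth of the two-year information.

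The second conflict has the same effect by another route. For two named events, one section keeps the subject under observation and another lets the site end participation. Two sites could handle identical subjects differently and both be within the protocol.

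**Working it through.** The contradictions are settled by setting the texts side by side. The arithmetic only sizes them.

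**1. Are the two end dates in Appendix 5 compatible?** Sections 7.5 and 7.6.2 rule out further transplants beyond 8 months after the first. The 2-years-after-initial assessment therefore falls between 24 − 8 = 16 and 24 months after the last transplant, which is always later than 12 months. The 2-years-after-last assessment falls at 24 months. Neither can be done if the last visit is at 12 months. A subject who stops at, say, month 15 would have a last visit dated before the discontinuation. Two years is the only reading that fits the rest of the document.

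**2. Contacts at stake.** The monthly contacts between months 12 and 24 number 24 − 12 = 12, so up to 12 per subject depend on which sentence is followed. As an illustration, assume a stop 3 months after the last transplant:

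| | To 12 months | To 24 months |
|---|---|---|
| Monthly SAE/hypoglycemia contacts | 12 − 3 = 9 | 24 − 3 = 21 |
| Interval alloantibody samples (months after stopping) | 1, 2, 3, 6, 9 = 5 | the same plus 12, 15, 18, 21 = 9 |

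**3. Routine SAE collection.** If a site treats the 12-month visit as completion, Section 8.3.1 carries routine collection to day 365 + 56 = 421, which is 730 − 421 = 309 days short of two years. Related SAEs and the events named in Section 8.2.2 remain reportable after that.

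**4. Precision.** Table 5 (Section 10.4) gives an upper 95% bound of 0.3085 for 0 of 10, and 1 − 0.025^(1/10) = 0.3085 reproduces it. Applying 1 − 0.025^(1/n) to a harm with no observed cases, with assumed numbers followed to two years:

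| n followed | Upper 95% bound |
|---|---|
| 10 | 30.9% |
| 8 | 36.9% |
| 7 | 41.0% |
| 5 | 52.2% |

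The protocol does not project how many subjects will enter reduced follow-up, so the lower rows are illustrations only.

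**5. Section 5.7.2 against Section 6.1.**

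| Event | 5.7.2 | 6.1 |
|---|---|---|
| Belatacept development ended | item 7: stops treatment, remains in study | item 4: may be terminated from study |
| Imprisonment or detention | item 8: stops treatment, remains in study | item 5: may be terminated from study |
| Adverse event or illness | item 4: stops treatment, remains in study | item 3: only if further participation itself is against the subject's interest |

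The third pair can be reconciled because Section 6.1 sets a higher threshold. The first two have no such distinction, and no text gives either section precedence.

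**The case against.** The best defence is that the 1-year sentence is an uncorrected remnant. The schedule beneath it names two years three times, so a careful site would follow that and lose nothing. Section 6.1 permits removal but does not require it. Both points stand: the loss is possible, not certain. They do not excuse leaving the sentence in place, since it is an explicit instruction on the last visit.

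Section 8.2.2 also stands, and it limits the consequence: the gravest events stay reportable to study end after drug is stopped. It schedules no contact to find them, however, and it speaks of stopping drug rather than of termination from the study.

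A reader might go further in four ways that the documents do not support.

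- *Half of the safety period is lost.* That treats a possible misreading as an accomplished fact.
- *The PTLD risk window is missed.* In the belatacept kidney studies "all but 1 occurred during the first 18 months post transplant", but the share arising after month 12 is not given. The clocks also differ: 12 months after the last transplant can be up to 8 + 12 = 20 months after the first. PTLD is named in Section 8.2.2, and the EBV-negative patients in whom the excess risk was concentrated are excluded from this trial.
- *All safety collection ends 56 days after removal under Section 6.1.* Section 8.3.1 still collects SAEs believed related. What ends is collection of adverse events generally and of SAEs not considered related.
- *The liver-transplant experience in Section 1.5.2 shows that the development-ended trigger is likely.* That section describes the end of one liver study, not of belatacept development, and says that causality was neither established nor excluded.

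**Conclusion.** Both contradictions are in the current text. Appendix 5 gives two end dates that cannot both be met, and the rest of the protocol agrees with two years. A site acting on the opening paragraph could close a discontinued subject up to 12 months early, at a cost of up to 12 monthly contacts and, for a stop at month 3, 4 of 9 interval alloantibody samples. The two-year hypoglycemia, sensitization and safety endpoints would then be incomplete for that subject. Scheduled detection, routine SAE collection and sampling are at risk; the duty to report the named grave events is not.

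Sections 5.7.2 and 6.1 conflict without a tie-breaker for two events. How many subjects either problem would affect cannot be derived from the document.

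This should be corrected. It does not touch the day-75 primary endpoint or its analysis.

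**What to change.** 1. In the opening paragraph of Appendix 5, change the last follow-up visit to two years after the last transplant, so that it agrees with the schedule below it, Section 7.5 and the two-year endpoints.
2. Reconcile Sections 5.7.2 and 6.1 for end of belatacept development and for detention by stating which rule governs, so that stopping study treatment does not by itself end follow-up where follow-up remains permitted.

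Both are wording changes by amendment. The 2-year assessments are already in the Appendix 5 schedule, so none is added. The cost is a few more contacts for subjects who would otherwise be closed out early.
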